## **Statistical analysis**

The demographic and baseline characteristics of the patients, vital signs, TISP, arterial blood gas indexes, and the perioperative outcomes could be divided into two types: categorical variables and continuous variables. The categorical variables were expressed by frequencies and proportions, and were analyzed by chi-square test or continuity correction chi-square test. The continuous variables were expressed by mean  $\pm$  SD, and were analyzed by t test or Fisher's exact test. All statistical analyses were 2 sided, and  $p < 0.05$  was considered statistically significant. Statistical analyses were performed by SPSS (IBM SPSS 28.0, SPSS Inc).

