## **Randomization**

The patients were randomly assigned to the CO2 group and O2 group at a 1:1 ratio. 52 opaque envelopes were made according to a random table generated by the PLAN process of SAS (SAS9.4, SAS Institute Inc). Each patient would receive an envelope which was opened by operators in surgery, when the structures of targeted segment were successfully dissected and anesthesiologist was about to re-expand the collapsed lung.

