## Outcome Measures

**Primary outcome:** The intersegmental border appearance time during the surgery.

**Secondary outcome:** Including BIS, arterial blood gases, arterial pressure and heart rate obtained when the patient was breathing room air (RA), the non-dependent lung was ready to be re-expanded when the bronchi and vessels of targeted segment had been dissected (0min), 3, 5, and 15 min after the non-dependent lung was fully inflated. Besides that, end-tidal carbon dioxide partial pressure (PetCO2) at 0, 3, 5, 15 min, duration of surgery, duration of drainage, total drainage, postoperative hospital stay, global Quality of Recovery 40 questionnaire (QoR-40) at 48 hours and 1 week after operation, postoperative complications (such as air leakage, pneumonia, atrial fibrillation, and all the postoperative complications were classified by the Clavien-Dindo classification of adverse events) were also included as secondary outcomes.

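### Complications get only arm proportions and a p-value; with about 26 patients per arm that output cannot show how large an excess is excluded, so a risk difference with a 95% confidence interval should lead

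*Combined protocol and SAP*

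**What the plan says.** The Outcome Measures section has one primary outcome: "The intersegmental border appearance time during the surgery". The list of secondary outcomes ends with "postoperative complications (such as air leakage, pneumonia, atrial fibrillation" and others, and adds that "all the postoperative complications were classified by the Clavien-Dindo classification of adverse events".

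The Statistical analysis section is a single paragraph. For categorical data it states: "The categorical variables were expressed by frequencies and proportions, and were analyzed by chi-square test or continuity correction chi-square test". It continues that "All statistical analyses were 2 sided" and sets the threshold at 0.05. It gives no risk difference, risk ratio, confidence interval or margin, no rule for choosing between the two chi-square tests, and no analysis of the Clavien-Dindo grades.

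The only sample-size figure is in the Randomization section: "52 opaque envelopes were made according to a random table". The same section says "The patients were randomly assigned to the CO2 group and O2 group at a 1:1 ratio". No power statement, target difference or expected complication rate appears anywhere.

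**The concern.** For an adverse outcome in a small trial, the useful question is how large an excess the data rule out. A significance test does not answer it. When few events are expected, a p-value above 0.05 is the likely result both when the arms do not differ and when one arm carries a moderate excess, so it does little to separate the two.

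What is at stake is how far the trial can speak about complications after re-expansion with CO2 rather than O2. With proportions and a p-value alone, the report would give no measure of the uncertainty around the difference, although the data needed for one will have been collected. The limit is shared by both chi-square tests and is not removed by choosing one of them.

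**Working it through.** **Inputs.**
- Patients per arm: 52/2 = 26, inferred from 52 envelopes at 1:1 (Randomization); the documents do not state it as such.
- Test: chi-square or continuity-corrected chi-square, two-sided, 0.05 (Statistical analysis).
- Control complication rate p: not in the documents. Assumed from 5% to 30%.
- Effect: a doubled risk, 2p. This is also an assumption.

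There is no plan figure to reproduce. The number 52 cannot be re-derived, because no effect size, standard deviation, event rate or power is given.

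**Power.** With a events on O2 and b on CO2, n = 26, N = 52 and t = a + b, the statistic is N·d²/[n²·t·(N − t)]. Here d = n·|b − a|, and the corrected test replaces d by max(0, d − N/2). Exact power is the sum of Bin(a; 26, p) × Bin(b; 26, 2p) over all pairs (a, b) with p-value below 0.05.

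| Assumed risks, O2 v CO2 | Corrected | Uncorrected | Doubling missed |
|---|---|---|---|
| 5% v 10% | 1.2% | 8.6% | 91-99% |
| 10% v 20% | 7.0% | 18.1% | 82-93% |
| 15% v 30% | 14.8% | 26.8% | 73-85% |
| 20% v 40% | 24.8% | 36.8% | 63-75% |
| 30% v 60% | 48.4% | 58.3% | 42-52% |

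Power reaches about 80% only near a 40% control rate (40% v 80%: 79.9% and 86.7%). Fisher's exact test would not help: 9.2% at 10% v 20%.

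**What significance would take.** With the corrected test:
- 0 v 6: d = 156 − 26 = 130, statistic 52 × 130²/(676 × 6 × 46) = 4.71, significant.
- 0 v 5: d = 130 − 26 = 104, statistic 52 × 104²/(676 × 5 × 47) = 3.54, p = 0.060, not significant. The uncorrected test on the same table gives 5.53, p = 0.019.
- With 3 events on O2, 11 are needed on CO2 (statistic 4.79); 10 give 3.69, below the critical value of 3.84.

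So with no events on O2, significance needs 6/26 = 23% on CO2. The 0 v 5 table, a 19-point difference, can be reported either way, because the plan does not say which test applies.

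**What an interval would show.** Newcombe's method combines the Wilson limits (l, u) of each arm. For the difference CO2 minus O2, the lower limit is D − √[(p₂ − l₂)² + (u₁ − p₁)²] and the upper is D + √[(u₂ − p₂)² + (p₁ − l₁)²].
- 3 v 3: each arm is 0.115 with Wilson limits 0.040 and 0.290. √(0.174² + 0.075²) = 0.190, so the interval is -19 to +19 points. The p-value is 1.0.
- 3 v 6: difference 3/26 = 11.5 points, interval -10 to +32; p = 0.27 uncorrected, 0.46 corrected.
- 0 v 5: difference 19 points, interval +2 to +38.
- 0 of 26 in one arm: exact two-sided upper limit 1 − 0.025^(1/26) = 0.132, or 13%.

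**The case against.** The strongest reply is that complications are one item at the end of a long secondary list, and a trial need not be powered for every secondary outcome. That is right, and low power alone is no criticism. It does make an interval the more useful output.

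A second reply is that arm frequencies are planned, so any reader can compute the interval, and the primary outcome and design are untouched. This also stands. The gap lies in the specified output. It biases no result and loses no data.

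A third reply is that harm is also assessed through Clavien-Dindo grading and through blood gases, arterial pressure, heart rate, BIS and end-tidal CO2 measured around the gas exposure. This is correct. But no analysis of the grades is described, and the physiological measurements do not supply a between-arm estimate for complications.

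Three stronger readings are tempting and not supported.
- A reader might infer that the trial intends to conclude safety from non-significance. The documents state no safety hypothesis, margin or such rule.
- A reader might infer that a doubled risk would almost always be missed. That depends on a control rate the documents do not give. It fits rates up to about 5%, or about 10% with the corrected test; at 15-20% the fair word is usually, and at 30% it is about half.
- A reader might infer that a non-significant result says nothing about harm. Very large excesses would probably be detected: from a 10% control rate, power is 80% for a CO2 rate of 42.5% (uncorrected) to 47.5% (corrected).

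**Conclusion.** The point holds as a limit of the planned output. Complications are analysed by proportions and a p-value with no estimate of the difference. At about 26 per arm, a non-significant result would usually be uninformative about a moderate excess, with power for a doubled risk between about 1% and 37% at control rates of 5% to 20%.

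This rests on three assumptions: the control rates, the doubling as the effect of interest, and 26 analysed per arm. The last may be optimistic: the Exclusion Criteria list conversion to thoracotomy in surgery, and applying that after the envelope is opened would lower the number analysed and widen the intervals. The absence of an estimate and interval does not depend on any of these assumptions. It is a cheap improvement worth making, and it does not call the primary comparison into question.

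**What to change.** In the Statistical analysis section:
- Make the risk difference (CO2 minus O2) with a Newcombe 95% confidence interval the main output for any postoperative complication, and separately for air leakage, pneumonia and atrial fibrillation.
- Label the chi-square p-values for complications as descriptive.
- State that any sentence about complications will rest on the interval, quoting the largest excess it does not exclude, and not on p > 0.05.

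The cost is about two sentences and routine output from data already collected, with no change to sample size, design or patient care. The downside is that statements about complications will look weaker, because intervals such as -19 to +19 points will be in view.

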## **Surgical Procedures:**

Before anesthesia induction, anesthesiologist placed the electrocardiogram, non-invasive blood pressure, pulse oximetry, bispectral index (BIS) monitor and completed radial artery catheterization successively. All patients were given general anesthesia with double lumen endotracheal intubation. After patients were placed in lateral decubitus position, one-lung ventilation of the dependent lung was initiated with 1.0 of FiO2 (fraction of inspiration) and 5 cm H2O of positive end-expiratory pressure. All patients underwent single-port thoracoscopic surgeries which were performed by the same surgical and anesthesia team. The surgical incision was about 3 cm long and located on the fourth or fifth intercostal space of the midaxillary line.

With the guidance of 3D reconstruction, the targeted segmental bronchi and vessels could be precisely identified and dissected, after that ISP was identified by modified inflation-deflation method. Firstly, anesthesia used fiberoptic bronchoscope to confirm the position and patency of endotracheal tube, suction if necessary. Then the non-dependent lung was re-expanded with airway pressure no more than 20 cm H2O and the flow of gas at 8 L/min, while the dependent ventilated lung was kept on mechanical ventilation without change. The non-dependent lung was re-expanded by pure O2 in O2 group, or by CO2 in CO2 group which was obtained from CO2 insufflator.

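### Blood gases are summarised only by arm means with SDs and a test, so the number of CO2 patients with a marked PaCO2 rise or pH fall could go unseen

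*Combined protocol and SAP*

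**What the plan says.** Under Surgical Procedures, the non-dependent lung is re-expanded with pure O2 in one arm, "or by CO2 in CO2 group which was obtained from CO2 insufflator". The gas flows at 8 L/min with airway pressure capped at 20 cm H2O, "while the dependent ventilated lung was kept on mechanical ventilation without change".

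Outcome Measures lists arterial blood gases as secondary outcomes at five times: on room air, at 0 min, and at 3, 5 and 15 min after full inflation. Complications are graded by Clavien-Dindo, but only postoperative ones. No PaCO2 or pH limit, worst value or intraoperative event is defined.

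The Statistical analysis section names the blood gas indexes among the variables to be analysed and sorts all variables into categorical and continuous. For the second type it says: "The continuous variables were expressed by mean $\pm$ SD, and were analyzed by t test". The sentence then offers Fisher's exact test as an alternative. Categorical variables get frequencies and proportions, but no blood gas category is defined to use that route. "All statistical analyses were 2 sided", at the 0.05 level.

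On size, the Randomization section says "52 opaque envelopes were made according to a random table", with patients "randomly assigned to the CO2 group and O2 group at a 1:1 ratio". No power calculation, SD or expected effect is given.

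**The concern.** CO2 retention and acidosis are the harms most directly tied to the experimental gas, and the three post-inflation samples measure them in each patient. The safety question that a reader will put beside a shorter border appearance time is how many patients had a large excursion, and how large. That question concerns the upper tail of PaCO2 and the lower tail of pH. A comparison of arm means answers a different question, namely whether the average moved.

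If the excursion is confined to a few patients, the mean moves little, those patients inflate the SD, and the test will usually be non-significant. If the whole arm moves, the test may well be significant, but a mean and a p-value do not separate a small uniform shift from a modest shift with several severe cases inside it. In neither case does the planned output give the number affected. The complication table does not supply it, because events during surgery are outside its scope.

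**Working it through.** The plan states no figure on this point, so there is none to reproduce. The check asks how a t test of means behaves when a few patients are severely affected.

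**Inputs from the documents.** 52 envelopes at 1:1 give 52/2 = 26 per arm if all are used. Tests are two-sided at 0.05.

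**Assumptions (the documents give no values).** Between-patient PaCO2 SD of 6, 8 or 10 mmHg; *k* CO2 patients shifted up by 25 mmHg; every CO2 patient also shifted by a common amount *c*.

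**Step 1: movement of the mean.** Shift in arm mean = *c* + 25*k*/26. With *c* = 0 this is 1.92, 2.88 and 3.85 mmHg for *k* = 2, 3 and 4.

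**Step 2: t test with no rise in the other CO2 patients** (simulation, 40,000 trials per setting; Welch within 0.01).

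| *k* of 26 | SD 6 | SD 8 | SD 10 |
|---|---|---|---|
| 2 | 8.7% | 7.5% | 6.9% |
| 3 | 15.6% | 12.9% | 10.9% |
| 4 | 26.8% | 20.5% | 16.8% |

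Hand check for *k* = 3, SD 8:
- CO2-arm variance ≈ 8² + 25² × (3/26)(23/26) × 26/25 = 64 + 66.4 = 130.4.
- Pooled SD = √[(64 + 130.4)/2] = 9.86; standard error = 9.86 × √(2/26) = 2.73.
- Difference needed for significance = 2.009 × 2.73 = 5.49 mmHg.
- With the affected patients fixed, the observed difference varies around 2.88 with SD 8 × √(2/26) = 2.22.
- P(Z > (5.49 − 2.88)/2.22) = P(Z > 1.18) ≈ 12%, close to the simulated 12.9%.

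**Step 3: the same 3 patients, with a rise *c* across the whole CO2 arm** (20,000 trials per setting).

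| *c* (mmHg) | SD 6 | SD 8 | SD 10 |
|---|---|---|---|
| 0 | 16% | 13% | 11% |
| 2 | 56% | 40% | 29% |
| 4 | 91% | 74% | 57% |
| 6 | 99% | 93% | 81% |

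The test result thus depends mainly on *c*, which the documents do not give. The number of severe cases is 3 in every row, and the planned summary does not report it in any of them.

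**Step 4: what the reported SD would show.** By the variance formula in Step 2, 3 affected patients raise the expected CO2-arm SD from 6, 8 and 10 to about 10.1, 11.4 and 12.9. Simulated medians were 10.0, 11.3 and 12.7, against 5.9, 7.9 and 9.9 in the O2 arm.

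**Step 5: what a patient count would show.** Exact (Clopper-Pearson) 95% intervals:
- 3/26 = 11.5%, interval 2.4% to 30.2%.
- 0/26: upper limit 1 − 0.025^(1/26) = 13.2%.

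A significance test of counts, with none in the O2 arm:

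| CO2 arm vs 0/26 | Fisher p | Continuity-corrected chi-square p |
|---|---|---|
| 3/26 | 0.24 | 0.23 |
| 5/26 | 0.051 | 0.060 |
| 6/26 | 0.023 | 0.030 |

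With either test, significance needs about 6 versus 0.

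**The case against.** The strongest reply is that a reader might infer that severe CO2 retention in a few patients will be averaged away and reported as no difference. The documents do not support that. It requires the other CO2 patients not to rise, yet all of them have the non-dependent lung re-expanded with CO2, so an arm-wide rise is at least as plausible. Step 3 shows that a shared 4 mmHg makes a significant result more likely than not at all three SDs. This stands, and it limits the claim to what could go unseen.

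Four further points are fair in part.

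- The SD is reported, and a wider CO2-arm SD would hint at a tail. The hint weakens as the underlying SD grows, and it does not tell how many patients were affected or in which direction.
- The plan mentions Fisher's exact test and has a route for categorical variables. Without a defined blood gas category, neither yields a count.
- A test of counts has little power too. That is correct, so the gain from counting is descriptive, and a rejection rate should not be set against a confidence interval as though they measured the same thing.
- The plan states no safety hypothesis or margin and does not announce a claim that CO2 was safe. A reader should not infer that it does; the caution about interpretation looks ahead to the report.

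Nor should a reader infer from Surgical Procedures that ventilation stays fixed through the 15 min sample. The words are attached to the re-expansion step, and the point here does not depend on them.

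**Conclusion.** The point holds as a gap in how safety data already collected are summarised. In the scenario with 3 of 26 affected and no rise in the others, about 84% to 89% of trials would show no significant difference in mean PaCO2. With a shared 4 mmHg rise, about 9% to 43% would. Whichever way the p-value falls, the planned summary does not say how many patients had a large excursion.

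These figures rest on 26 per arm, an SD of 6 to 10 mmHg, a 25 mmHg excursion and the stated common shifts. Only the first is inferred from the documents; the others are assumptions. The absence of any worst value, range or patient count can be read directly in the text and depends on none of them.

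The consequence is moderate. It concerns secondary outcomes and leaves the analysis of border appearance time untouched. It is worth correcting because the blood gases carry the main safety information specific to this gas.

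**What to change.** Add to the Statistical analysis section, for arterial blood gases:

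> For each patient, the highest PaCO2 and the lowest pH over the samples at 3, 5 and 15 min will be taken. By arm, the median and full range of these worst values will be reported, together with the number and percentage of patients beyond limits fixed by the anesthesia team before the data are analysed, with exact 95% confidence intervals. These summaries are descriptive. Mean and SD by time point will be reported as planned. A non-significant t test of means will not be read as evidence that CO2 was safe.

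The choice of limits is a clinical matter and none is proposed here. The median and range need no limit, so they remain usable even if agreement on limits is slow.

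The cost is a paragraph and one table from data already collected, with no new samples, staff or patients. The downsides are that the limits must be settled in advance and that the intervals will be wide: even 0/26 leaves an upper limit of 13.2%, so the safety statement may read less favourably than a non-significant p-value would.
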